12.4 Analysis of Endpoints

12.4.1 Analysis of Primary Endpoints

To assess the primary endpoint of improvement of pain on a visual analog scale (VAS) between pre-op, 1, 2, and 3 months post-op, a repeated measure of analysis of variance will be performed with one between subject factor (botulinum toxin A versus placebo) and one within subject factor (time). In the event of significant loss to follow-up, we will explore the use of a linear mixed model to assess the independent effect of the study group on VAS over the study visits.

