	analog scale prior to treatment and at one, two and three months post-			
	treatment in both the Botox and placebo groups.			
Secondary Objectives:	The secondary objectives will be to compare the quality of life (SF-36),			
	maximum interincisal opening, and functional status via the jaw			
	functional limitation scale in both the Botox and placebo groups.			
Exploratory Objectives:	None			
Endpoints:	The primary endpoint is improvement of pain on a visual analog scale			
	(VAS) between pre-op, 1, 2, and 3 months post-op. The secondary			
	endpoints are function (MIO/jaw limitation scale) and quality of life			
	(SF36)			

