1.1 Schema

Prior to Enrollment Total 110 participants: Obtain informed consent. Screen potential participants by inclusion and exclusion criteria; obtain history, document.

Visit 1 Day 0 Perform baseline assessments: Inclusion/exclusion checklist, pre-operative assessment (maximum interincisal opening), jaw functional limitation scale, visual analog scale, and SF-36 questionnaire

Administer study drug.

T

[figure not shown]
Visit 2 1 – Month

Follow-up assessments of study endpoints and safety: Follow-up assessment (maximum interincisal opening), jaw functional limitation scale, visual analog scale, and SF-36 questionnaire

 Ω

Visit 3 2 – Months

Follow-up assessments of study endpoints and safety: Follow-up assessment (maximum interincisal opening), jaw functional limitation scale, visual analog scale, and SF-36 questionnaire

Page # 11

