4.2 Inclusion Criteria

- 1. 18 65 years of age
- 2. Able to give informed consent
- 3. Myofascial pain of masticatory muscles as defined according to the RDC/TMD criteria
- 4. Baseline pain measured by the subject ≥ 3.5/10 on visual analog scale

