12.1 Study Design/Endpoints

Based on the preliminary data and the sample size calculations estimating a difference in mean prepost VAS change between groups of 1 point or greater (on a scale of 1-10), we plan to enroll a total of 110 subjects between the two study sites. Estimated 55 subjects will be enrolled at Weill-Cornell Medical Center/ New York Presbyterian Hospital and 55 subjects will be enrolled at the University of Illinois at Chicago. With 55 patients in the botulinum toxin A injection group and 55 patients in the placebo group (N=110), the study will have more than 90% power to detect a difference in mean in pre-post change between groups of 1.0 point or greater on VAS, using a two-sided t-test and assuming a standard deviation of 1.5 for the mean difference. This calculation allows for 10% attrition rate.

An intent-to-treat design will be followed and all subjects will have scheduled outcome evaluations until the end of the study, death of the subject, or subject refusal. Subjects will be withdrawn from their randomly assigned treatment for considerations of subject safety only. Descriptive statistics including mean, standard deviation, median, range, frequency, and percent will be calculated for the entire cohort as well as by the study arm (botulinum toxin A and unpreserved 0.9% sodium chloride) to assess the results of randomization and identify potential confounders.

The primary analyses of the data will be performed according to subjects' original treatment assignment (i.e., intention-to-treat analyses) and the inclusion of all data from all subjects randomized in the final analysis. To assess the primary endpoint of improvement of pain on a visual analog scale (VAS) between pre-op, 1, 2, and 3 months post-op, a repeated measure of analysis of variance will be performed with one between subject factor (botulinum toxin A versus placebo) and one within subject factor (time). This analysis will also be used for the secondary endpoints: function (MIO/jaw limitation scale) and quality of life (SF12). In the event of significant loss to follow-up, we will explore the use of a linear mixed model to assess the independent effect of the study group on VAS over the study visits. The paired t-test, or the signed-rank test as appropriate, will be used to assess change in pain, function, and QOL between pairs of relevant time points for both study arms.

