12.4.2 Analysis of Secondary Endpoints

The same analysis as that of the primary endpoints will also be used for the secondary endpoints: function (MIO/jaw limitation scale) and quality of life (SF36).

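### The primary repeated-measures ANOVA appears to treat pre-op VAS as an outcome rather than a covariate, and no between-arm test is named as the one that decides the primary endpoint

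*Combined protocol and SAP*

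**What the plan says.** Sections 12.1 and 12.4.1 give the same primary analysis: "improvement of pain on a visual analog scale (VAS) between pre-op, 1, 2, and 3 months post-op, a repeated measure of analysis of variance", with "one between subject factor (botulinum toxin A versus placebo) and one within subject factor (time"). Pre-op is listed beside the three follow-up visits, and no covariate appears in either section. If loss to follow-up is significant, the team will explore a "linear mixed model to assess the independent effect of the study group on VAS over the study visits".

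The power statement in Section 12.1 rests on a different test. It claims to exceed "90% power to detect a difference in mean in pre-post change between groups of 1.0 point or greater on VAS, using a two-sided t-test", with an SD of 1.5, 55 per arm and 10% attrition. It does not say which follow-up visit supplies the post value.

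Section 12.1 also plans paired t-tests or signed-rank tests between time points, which look at change within each arm. Section 12.4.2 extends the model: "The same analysis as that of the primary endpoints will also be used for the secondary endpoints".

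Pre-op VAS is available for every treated patient. The schema for Visit 1 reads "Perform baseline assessments: Inclusion/exclusion checklist, pre-operative assessment (maximum interincisal opening), jaw functional limitation scale, visual analog scale, and SF-36 questionnaire", all before the injection, and Section 4.2 makes it an entry criterion: "Baseline pain measured by the subject ≥ 3.5/10 on visual analog scale".

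**The concern.** A two-factor repeated-measures ANOVA yields a group main effect, a time effect and a group-by-time interaction, and several contrasts can be added. The group main effect and the interaction both compare the arms, but they answer different questions, and the plan does not say which one settles the trial.

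The wording points in two directions. The synopsis says "The primary endpoint is improvement of pain on a visual analog scale", the power statement speaks of pre-post change, and Section 3.1 hypothesises a greater reduction than with placebo. These favour group-by-time. The wording of the mixed-model fallback can be read as the group main effect. With pre-op as a level, that main effect averages in a visit at which no treatment effect can exist, so it is diluted.

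Three things are at stake:

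- **Error control.** Section 7.11 unblinds the study team after follow-up, and a test not named by then can be chosen with the results in view.
- **The power claim.** It belongs to a test that is not the planned primary analysis.
- **Precision.** A prognostic measurement already taken in every patient is left unused as a covariate.

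**Working it through.** **Inputs from Section 12.1:** difference 1.0, SD of change 1.5, two-sided alpha 0.05, 55 per arm, 10% attrition. 55 × 0.9 = 49.5, taken as n = 49 per arm.

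**Assumptions:** the documents give no visit-to-visit correlation or time course. I take compound symmetry with correlation r = 0.3, 0.5 or 0.7, and several patterns of benefit at months 1/2/3. The VAS variance is set so that the SD of change stays at 1.5: s² = 1.5²/(2(1−r)), which gives 1.607, 2.25 and 3.75.

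**1. The plan's own figure.** Two-sample t-test, noncentral t, effect 1.0/1.5: 93.4% at 55 per arm and 90.4% at 49. The stated power reproduces for a t-test on one pre-post change.

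**2. Group-by-time.** F with 3 and 3(2n−2) df; λ = (n/2) × Σ(centred effects²)/(s²(1−r)). Here s²(1−r) = 1.125 at every r. For effects 0, 1, 1, 1 the centred sum of squares is 0.75, so λ = 24.5 × 0.75/1.125 = 16.33 and power is 93.6%. For 0, 0.5, 1.0, 0.5 the sum is 0.5, so λ = 10.89 and power is 79.3%.

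**3. Group main effect over four visits, pre-op included.** A constant 1.0 benefit becomes (0+1+1+1)/4 = 0.75. The variance of the patient mean is s²(1+3r)/4. At r = 0.7 this is 3.75 × 3.1/4 = 2.906 (SD 1.705). Power is 98.8, 87.3 and 57.8% for r = 0.3, 0.5 and 0.7.

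**4. Joint baseline-adjusted test at months 1 to 3.** Residual covariance S = s²[(1−r)I + (r−r²)J]; λ = (n/2)d′S⁻¹d; F with 3 and 2n−5 df. For a constant 1.0 at r = 0.5: λ = 24.5 × 3/(2.25 × (0.5 + 3 × 0.25)) = 26.1, power 99.3%.

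**5. Baseline-adjusted average of months 1 to 3.** t-test with variance s²[(1+2r)/3 − r²].

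Power (%) at 49 per arm; three values are for r = 0.3/0.5/0.7:

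| Benefit at months 1/2/3 | Group-by-time | Joint, adjusted | Average, adjusted |
|---|---|---|---|
| 1.0/1.0/1.0 | 93.6 | 99.9/99.3/97.6 | at least 99.5 |
| 0.5/1.0/0.5 | 79.3 | 96.0/90.9/85.5 | 97/92/86 |
| 1.0/0.5/0 | 91.3 | 96.5/94.4/92.6 | 83/72/62 |
| 0/0/1.0 | 93.6 | 95.5/94.4/93.7 | 49/39/33 |

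**6. Alternative reading.** If the ANOVA were run on change scores at months 1 to 3, its group term would have variance 4s²(1−r)/3 = 1.5. It would not be diluted, and power for the constant effect would be 97.9%.

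**7. Choosing the test afterwards.** If either the group main effect or group-by-time could be declared the result at 0.05, simulated false positives are 9.2 to 9.6% (4,000 trials per correlation, 55 per arm). Two independent tests would give 1 − 0.95² = 9.75%. Adding the three monthly between-arm tests on change raises the rate to about 17%.

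**8. Sensitivity** (20,000 simulated trials per cell, 49 per arm; three values follow the correlation in order).

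- *Correlation decaying with time* (AR(1) 0.5/0.7/0.85), joint test against Greenhouse-Geisser group-by-time. Constant effect: 100.0/99.9/99.8% against 97.4/98.0/98.7%. Effect 0.5/1.0/0.5: 97.2/96.9/97.5% against 87.6/90.3/92.2%. Without that correction, group-by-time has 5.7 to 6.6% false positives.
- *Entry cut-off of 3.5 applied* (mean 5.5 before the cut, assumed; r = 0.3/0.5/0.7), joint test against uncorrected group-by-time. Constant effect: 99.8/98.7/96.8% against 93.3/93.3/93.7%. Effect 0.5/1.0/0.5: 94.0/88.2/82.1% against 78%. Month 3 only: 93.1/92.1/91.7% against 91.9/92.0/92.6%, so no real gain.

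False positives for the joint test were 4.8 to 5.2% throughout.

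**The case against.** The planned model is a standard, valid one. On the reading the documents favour, group-by-time has 93.6% power for the constant 1.0-point effect after attrition, which meets the stated target. The 58% figure needs both the less likely reading and a correlation of 0.7; at 0.3 the main effect has 98.8%, which is better than group-by-time. The fallback wording belongs to an analysis that is only to be explored, so it is weak evidence of how the main ANOVA would be read. Having pre-op in the outcome vector is not itself the fault: a longitudinal model that constrains the arm means to be equal at baseline is about as efficient as covariate adjustment. The gain from adjustment also depends on assumed patterns and is close to nil for a month-3-only effect. An averaged contrast can do much worse than the existing plan.

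All of this stands, and it limits the size of the problem. It does not supply the missing choice. The t-test only sizes the trial, the paired tests do not compare arms, and the mixed model carries no stated contrast. Nor does it remove the gain from adjustment. In the cases checked the joint test matches or beats group-by-time, apart from about 1 point lost for a month-3-only effect at high correlation with the entry cut-off applied.

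**Conclusion.** The point holds and should be fixed. It is certain from the text that no deciding between-arm test is named and no baseline covariate is listed. That pre-op is a time level is the natural reading, though not the only possible one.

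The size of the harm depends on the reading, the correlation and the time course. Under group-by-time the loss is moderate: about 4 to 6 points for a constant 1.0-point benefit and 6 to 17 points for 0.5/1.0/0.5 under compound symmetry, with smaller gaps when correlation decays with time. It is large only if the group main effect is taken with pre-op included. The sample size is not wrong on its own inputs; the power statement simply describes another test. The same gap passes to the secondary endpoints.

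**What to change.** In Sections 12.1 and 12.4.1, model VAS at months 1, 2 and 3 with arm, month, arm-by-month and pre-op VAS as a covariate, its slope allowed to differ by month, and an unstructured covariance. Before unblinding, name one between-arm test as primary:

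- **(a)** the joint test of the baseline-adjusted arm differences at months 1 to 3, reported with the monthly differences and 95% confidence intervals; or
- **(b)** a single contrast that matches the expected time course, such as the average over months 1 to 3 if a sustained effect is expected.

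The choice is the sponsor's. Test (a) is robust across the patterns examined but gives no single effect size. Contrast (b), as an average, gives one effect size but is a trade-off: its power falls to 62–83% for 1.0/0.5/0 and 33–49% for an effect at month 3 only.

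Restate power for the chosen test with the assumed correlation given; whether 110 patients still provide 90% depends on both. Use the same model for each secondary endpoint with its own pre-op value as covariate, and state that the within-arm paired tests are not a comparison of arms.

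The cost is SAP wording and SAS code, with no new data, visits or patients. The minimum fix is one sentence naming group-by-time as the deciding term. It removes the ambiguity but leaves the gain from baseline adjustment unused.

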To assess the difference in proportion of adverse events between the botulinum toxin A and placebo groups, either the chi-square or Fisher's exact test will be used, as appropriate. All p-values will be two-sided with statistical significance evaluated at the 0.05 alpha level. Ninety-five percent confidence intervals (95% CI) will be calculated to assess the precision of the obtained estimates.

All analyses will be performed in SAS Version 9.4 (SAS Institute Inc., Cary, NC). Note: This section was drafted in conjunction with [name] and [name] in the Division of Biostatistics and Epidemiology, Department of Healthcare Policy and Research. They will be aiding in protocol design and development, data management, study implementation, study monitoring, and data analysis and reporting.

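### The primary repeated-measures ANOVA states no sphericity correction, covariance structure or contrast error term, so intervals for the BTA–placebo difference in change could be miscalibrated in either direction

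*Combined protocol and SAP*

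**What the plan says.** Section 12.4.1 (repeated in 12.1) defines the primary endpoint as "improvement of pain on a visual analog scale (VAS) between pre-op, 1, 2, and 3 months post-op" and states that "a repeated measure of analysis of variance will be performed with one between subject factor (botulinum toxin A versus placebo") and with time as the one within-subject factor. The natural reading is a group-by-time ANOVA with four time levels, the first being the value before injection. Section 12.4.2 adds: "The same analysis as that of the primary endpoints will also be used for the secondary endpoints".

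The only other longitudinal model is conditional: "In the event of significant loss to follow-up, we will explore the use of a linear mixed model". Its trigger is missing data, not the pattern of variances and correlations, and no covariance structure is named for it.

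On inference, section 12.1 says "All p-values will be two-sided with statistical significance evaluated at the 0.05 alpha level" and "Ninety-five percent confidence intervals (95% CI) will be calculated to assess the precision of the obtained estimates". It does not say which estimates get intervals or which error term supplies the standard error. The sample size in the same section rests on a two-sample t-test of change, with "more than 90% power to detect a difference in mean in pre-post change between groups of 1.0 point or greater on VAS" and an SD of 1.5.

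Neither section 12.1 nor 12.4 mentions a sphericity check, a Greenhouse-Geisser or similar correction, a multivariate test, or a covariance structure.

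**The concern.** The classical ANOVA has one within-subject error term. It averages the variability of all six visit-to-visit differences: three between baseline and a follow-up, and three between follow-ups. The trial's question concerns only the first kind. If the two kinds differ in variability, a contrast in change from baseline that uses the averaged error has the wrong standard error.

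The design gives a reason to expect unequal variability. A single injection separates baseline from three visits that all follow it, so follow-up scores may well correlate more with each other than with baseline. Correlation may also decay with time, in which case month 1 and month 3 differ from baseline by different amounts. What is at stake is the coverage of the main treatment-effect interval, the false-positive rate of visit-specific contrasts, and the same quantities for mouth opening, jaw function and quality of life.

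**Working it through.** **The plan's own figure.** Inputs from 12.1: difference 1.0, SD 1.5, two-sided 0.05, 55 per arm, 10% attrition. With the t-test, power is 93.4% at 55 per arm and 90.4% at 49. The smallest n for 90% is 49 per arm, and 49/0.9 = 54.4, rounded up to 55, so N = 110. The figure reproduces. It uses the SD of the change score itself, not a pooled ANOVA error.

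**Formula.** For a 4×4 covariance S, the expected within-subject mean square is MSE = tr(CSC)/3, with C the centring matrix. Twice this equals the mean of the six pairwise difference variances. For month t minus baseline:

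ratio (pooled SE / own SE) = √[2·MSE / Var(Y_t − Y_0)].

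The approximate false-positive rate is 2Φ(−1.96 × ratio).

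**Inputs that are assumptions.** The documents give no visit SDs or between-visit correlations. All covariances below are assumed.

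*Decaying correlation, AR(1) 0.7, SD 2 at every visit.* Difference variances are 8(1 − 0.7) = 2.40 at lag 1, 8(1 − 0.49) = 4.08 at lag 2 and 8(1 − 0.343) = 5.26 at lag 3. Their mean over the six pairs is (3×2.40 + 2×4.08 + 5.26)/6 = 3.44. Ratios: √(3.44/2.40) = 1.20 at month 1, √(3.44/4.08) = 0.92 at month 2, √(3.44/5.26) = 0.81 at month 3.

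*Follow-ups more alike, baseline r 0.3, follow-up r 0.6, SD 2.* Baseline-to-month variance is 8×0.7 = 5.60 and month-to-month is 8×0.4 = 3.20; the mean is 4.40. Ratio √(4.40/5.60) = 0.89 at each visit.

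*Common correlation 0.5, baseline SD 1.5, follow-up SD 2.3.* Baseline-to-month variance is 2.25 + 5.29 − 3.45 = 4.09 and month-to-month is 5.29; the mean is 4.69. Ratio √(4.69/4.09) = 1.07.

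Coverage of nominal 95% pooled-error intervals, from 6,000 simulated trials each with 55 per arm and no treatment difference:

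| Assumed covariance | Ratio, months 1 / 2 / 3 | Coverage, months 1 / 2 / 3 |
|---|---|---|
| Equal SD, common r 0.5 | 1.00 / 1.00 / 1.00 | 95.1 / 94.3 / 94.9% |
| AR(1) 0.7, equal SD | 1.20 / 0.92 / 0.81 | 97.9 / 92.8 / 88.2% |
| r 0.3 with baseline, 0.6 among follow-ups, equal SD | 0.89 each | 91.9 / 92.5 / 92.1% |
| r 0.3 and 0.7, SD 1.5 then 2.3 | 0.89 each | 92.0 / 91.9 / 91.9% |
| Common r 0.5, SD 1.5 then 2.3 | 1.07 each | 96.6 / 96.4 / 96.4% |
| Common r 0.3, SD 1.5 then 2.3 | 1.08 each | 96.7 / 96.5 / 96.8% |

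With each contrast's own error, coverage was 94.4–95.5% in every row.

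**Extremes.** For mean follow-up minus baseline, the third row gives a ratio of 0.80 (coverage 89.1%). AR(1) 0.75 with equal SDs has relative difference variances of 0.250, 0.4375 and 0.578 at lags 1 to 3. Their mean is (3×0.250 + 2×0.4375 + 0.578)/6 = 0.367, so the ratio is √(0.367/0.250) = 1.21 at month 1 and √(0.367/0.578) = 0.80 at month 3. A ratio of 0.80 gives 2Φ(−1.57) = 0.12.

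**On the plan's scale.** If the SD of change at a visit is 1.5, the correct half-width at 55 per arm is 1.98 × 1.5 × √(2/55) = 0.57. Ratios of 0.80 and 1.20 turn this into 0.46 and 0.68 VAS points.

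**Overall group-by-time F test, uncorrected.** It rejected in 5.0–6.2% of the simulations above. With 20,000 trials per scenario, 50 per arm and baseline cut to 3.5–10, it rejected in 5.2–6.8%, or 4.7–4.9% with the Greenhouse-Geisser correction.

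**Entry floor alone.** Let ρ be the common correlation, σ² the variance before selection, and k < 1 the fraction of baseline variance left after truncation. Then Var(Y_t − Y_0) − Var(Y_s − Y_t) = −(1 − ρ)²(1 − k)σ², which is negative. With parent mean 5, SD 2, ρ 0.5 and k 0.56, this is −0.25×0.44×4 = −0.44. The variances are 3.56 and 4.00, their mean is 3.78, and the ratio is √(3.78/3.56) = 1.03: slightly too wide.

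**The case against.** A reader might infer that the design violates sphericity and that the planned intervals are therefore too narrow, with the entry rule ("Baseline pain measured by the subject ≥ 3.5/10 on visual analog scale") as one of the causes. The documents do not support this.

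- **Violation is not shown.** No visit-specific SD or correlation is reported. Non-sphericity is plausible, not demonstrated.
- **Narrowness is not the only direction.** It arises when follow-ups correlate clearly more with each other than with baseline, or at month 3 under decaying correlation. It reverses at month 1 under decaying correlation, and with a common correlation when follow-up SDs exceed the baseline SD.
- **The entry floor works the other way.** Taken alone it makes pooled-error intervals slightly too wide.
- **Use of the pooled error is an inference from the model's name.** Section 12.1 leaves the interval method open, and its t-test for sample size and its paired tests each use their own error.
- **The overall interaction test is little affected.**
- **A mixed model is already mentioned.**

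The first five points stand and limit the claim. They do not remove it. The paired tests are within arm and do not supply the between-arm interval. The mixed model is only to be explored, on a missing-data trigger, with no structure named. An open interval method leaves the error term to be chosen at analysis, when the choice can move the interval width by about a fifth either way.

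**Conclusion.** The concern holds as one of an unprotected and under-specified primary method, not as a demonstrated bias in one direction. The size depends on two things that the documents leave open: whether the pooled error is used for the between-arm contrasts, and the true covariance of the four VAS scores. Over the patterns examined, visit-level or average-change standard errors run from about 0.80 to about 1.20 times their correct value. At the narrow end that means up to about 12% false positives. With equal variances and a common correlation there is no error at all.

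The secondary endpoints inherit the method, but none was modelled here, so no size is claimed for them. The sample-size calculation is sound and unaffected. The point is worth acting on because a better method costs almost nothing and holds its coverage whatever the covariance turns out to be.

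**What to change.** In 12.1, 12.4.1 and 12.4.2, make the primary model a repeated-measures model with unstructured covariance across the four visits (SAS PROC MIXED, REML, Kenward-Roger degrees of freedom). State that each BTA–placebo difference in change from baseline, with its 95% interval, is taken from this model. Use it regardless of the amount of loss to follow-up.

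If the ANOVA is kept, specify that each between-arm difference in change is tested and interval-estimated with its own error term, and that the group-by-time test is reported with the Greenhouse-Geisser correction.

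The cost is SAP wording and a few more covariance parameters: 4×5/2 = 10 for an unstructured matrix against 2 for compound symmetry. SAS 9.4 is already named. N = 110 and the stated power do not change, because they already rest on the SD of the change score. Intervals may become wider or narrower than pooled-error ones, according to the visit.
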